5.5.3 Primary Inferential Analysis

5.5.3.1 Incidence Rate Ratio (IRR) Estimation

The primary inferential analysis will evaluate the incidence rates of AEs following the influenza vaccines, comparing the rates of AEs in the risk and control intervals using a conditional Poisson regression model, conditioning on the total number of AEs observed for an individual patient in the observation period. This analysis will be restricted to the case population and conducted for each AE for influenza vaccines overall and by high-dose and adjuvanted vaccine groups.

The main primary analysis model will include a Farrington, seasonality and positive predictive value (PPV) adjustment (for AEs with PPVs available based on medical record review). The Farrington adjustment will be used to account for the reduced observation time that can occur from the occurrence of an event.⁽²⁷⁾ A separate analysis will be conducted including Farrington and PPV adjustments only, to evaluate the independent effect of the PPV adjustment excluding the seasonality adjustment. Another separate analysis will be performed including Farrington and seasonality adjustments only to evaluate

³ Covariate will be based on Health and Human Service (HHS) Region as specified on <https://www.hhs.gov/about/agencies/iea/regional-offices/region-1/index.html>

⁴ Beneficiaries' immunocompromised status will be determined based on a CBER-modified algorithm adapted from the Greenberg et al. algorithm, which was developed and validated to identify immunocompromised persons. Details on the algorithm can be found in Appendix 10.21.

the independent effect of the seasonality adjustment. The approach for the seasonality and PPV adjustments are specified in Section 5.5.5.

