5.5.5.2 Positive Predictive Value (PPV) Adjustment Analysis

For certain AEs with PPVs available from prior medical record review (anaphylaxis and GBS), a PPV-adjustment will be included in the model for both primary and follow-up analyses to ascertain IRR estimates that account for potential outcome misclassification related to the claims-based AE definition. Table 5 presents the PPV estimates that will be used for the adjustment based on medical record review findings from previously published studies using a CMS population. IRRs directly obtained from primary and follow-up analyses without a PPV adjustment may be biased, as a portion of the cases identified during the observation period may not be true cases. PPV-adjusted models will be implemented including the Farrington adjustment only, and in a combined model including both Farrington and seasonality adjustments.

Table 5. AE Positive Predictive Value (PPV) Estimates from Prior Medical Record Review

AE (Setting)	PPV (95% CI)
Anaphylaxis (IP, OP-ED)	66% (95% CI: 56%, 76%) ⁽³⁴⁾
GBS (IP, primary diagnosis position)	71% (95% CI: 63%, 79%) ⁽³⁵⁾

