5.5.6 Attributable Risk (AR) Estimation

For the primary analyses and when follow-up analyses apply, the study will also estimate an adjusted AR statistic (per 100,000 vaccinations). The AR is the excess number of AE cases divided by the number of eligible beneficiaries (or eligible follow up dose-years). The number of excess AE cases due to the influenza vaccine will be derived directly from the conditional Poisson regression model, defined as the difference between the sum of the model fitted values (i.e., model predicted number of cases), and the sum of the expected cases (i.e., all observed time is treated as control time). The standard error (SE) of the AR is estimated by bootstrap resampling 10,000 times. For each iteration, this study will sample the beneficiaries with AE with replacement and repeat the AR calculation. The SE is calculated as the square root of the variance of the 10,000 AR values. AR estimates will be reported for each of the AEs for influenza vaccines overall, and by high-dose and adjuvanted vaccine groups separately.

6. Medical Record Review

For AEs without PPVs available from previous medical record review, medical record review may be considered if a significant elevation in incidence rates is detected from the study. The purpose of medical record review will be to evaluate the accuracy of the claims-based outcome definition(s) used. AE-specific PPVs and 95% CIs will be estimated to assess the probability of event misclassification based on the claims-based definitions used.

7. Ethical Evaluation

This public health surveillance activity is conducted as part of the FDA CBER BEST Initiative under the FDA Amendments Act of 2007. This study uses Medicare administrative claims data. The study involves no personal health information; no direct intervention on study participants; data used in this study is de-identified and anonymized before its use; the analysis is conducted in a Federal Information Security Management Act compliant environment; and the results are presented in aggregate.

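### The attributable-risk SE in Section 5.5.6 has no step for the sampling error of the external PPVs; if the PPV scales the AR, the SE is too small, mainly for anaphylaxis with a clear excess

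*Protocol*

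**What the plan says.** Section 5.5.6 defines the estimate: "The AR is the excess number of AE cases divided by the number of eligible beneficiaries (or eligible follow up dose-years"). The excess is "derived directly from the conditional Poisson regression model", as summed fitted cases minus the cases expected if all time were control time. The SE is then set out from start to finish, with 10,000 bootstrap iterations. On what varies between them, the section says: "For each iteration, this study will sample the beneficiaries with AE with replacement and repeat the AR calculation". The standard deviation of the resulting AR values is the SE. Case resampling is the only random step named.

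Section 5.5.3.1 says: "The main primary analysis model will include a Farrington, seasonality and positive predictive value (PPV) adjustment", for AEs with a PPV from record review. Section 5.5.5.2 names these as anaphylaxis and GBS and gives the source of the values: "Table 5 presents the PPV estimates that will be used for the adjustment based on medical record review findings". Table 5 lists 66% (95% CI 56% to 76%) for anaphylaxis and 71% (95% CI 63% to 79%) for GBS. The protocol does not say whether these intervals enter the variance of the IRR or the AR.

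**The concern.** The PPVs come from earlier chart reviews, so they have sampling error of their own. Resampling this study's cases cannot reproduce it, because that error arose in other samples. If the AR is proportional to the PPV, its relative SE cannot fall below that of the PPV, however many vaccinees are studied. The procedure as written lets the SE shrink with the case count alone.

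The AR per 100,000 vaccinations is reported for every AE, overall and by vaccine group. The understatement grows with the strength of the signal, so it is largest when readers would rely most on the AR.

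**Working it through.** The protocol states no AR, SE, case count or IRR, so it has no figure of its own to reproduce. Case counts and IRRs below are assumptions, shown as a range.

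**Inputs.** PPVs and intervals are from Table 5. Interval lengths are from Table 4: anaphylaxis 2 risk days and 14 control days, GBS 42 and 48 days. The time ratio k is therefore 2/14 = 0.143 and 42/48 = 0.875.

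**PPV error.** SE = CI width / 3.92.
- Anaphylaxis: 0.20/3.92 = 0.051; CV = 0.051/0.66 = 7.7%.
- GBS: 0.16/3.92 = 0.041; CV = 0.041/0.71 = 5.7%.

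**Assumed mechanism.** AR = PPV × excess / N, with one PPV for both intervals. With n cases, the share in the risk interval is p = IRR·k/(1 + IRR·k). The excess is n[p − k(1 − p)], and its case-only bootstrap SE is (1 + k)·sqrt(n·p(1 − p)). Z is their ratio; a constant PPV cancels from it.

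**Missing PPV component.** For a product of independent estimates, the SE with the PPV drawn, divided by the SE with the PPV constant, is sqrt(1 + CV²(Z² + 1)).
- At Z = 2: 1.015 for anaphylaxis and 1.008 for GBS.
- At Z = 5: 1.07 and 1.04.
- At Z = 10: 1.27 and 1.15.

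**Missing count component.** Resampling n cases with replacement fixes the total at n. If the total varies as a Poisson count, the variance of the excess gains excess²/n, a factor of sqrt(1 + Z²/n) on the SE. This exceeds the PPV term when 1/n > CV², that is, below about 167 cases (anaphylaxis) or 303 cases (GBS).

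**Example** (anaphylaxis, 100 cases, IRR 5). p = 0.714/1.714 = 0.417. Excess = 100 × (0.417 − 0.143 × 0.583) = 33.3. Case-only SE = 1.143 × sqrt(100 × 0.417 × 0.583) = 5.63. Z = 5.9. PPV factor = sqrt(1 + 0.00598 × 36.0) = 1.10. Count factor = sqrt(1 + 35.0/100) = 1.16.

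| AE | Assumed IRR | Assumed cases | Z | PPV factor | Count factor | Both |
|---|---|---|---|---|---|---|
| Anaphylaxis | 2 | 100 | 2.3 | 1.02 | 1.03 | 1.05 |
| Anaphylaxis | 3 | 100 | 3.8 | 1.05 | 1.07 | 1.11 |
| Anaphylaxis | 5 | 100 | 5.9 | 1.10 | 1.16 | 1.25 |
| Anaphylaxis | 5 | 200 | 8.4 | 1.19 | 1.16 | 1.33 |
| Anaphylaxis | 10 | 160 | 11.9 | 1.36 | 1.37 | 1.66 |
| GBS | 1.5 | 150 | 2.5 | 1.01 | 1.02 | 1.03 |
| GBS | 2 | 150 | 4.3 | 1.03 | 1.06 | 1.09 |

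If a nominal 95% interval were built from an SE that omits only the PPV component, its coverage would be about 92% for anaphylaxis at IRR 5 with 100 cases and about 90% with 200. For GBS at IRR 1.5 with 200 cases it would be about 94.6%.

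**The case against.** A reader might infer that the protocol fixes the PPV as a known constant. It does not say so. Section 5.5.6 never mentions the PPV, and repeating the AR calculation could in principle include a PPV draw. A constant PPV is the natural reading of a tabulated value, but it remains an inference. What the text supports is that no step for PPV uncertainty is specified.

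The mechanism is also open. The model formula in Section 5.5.5.1 has no PPV term. Section 5.5.5.2 presents the adjustment as correcting possible bias in the IRR, whereas one PPV common to both intervals would leave the IRR unchanged. The sizes above therefore depend on an assumed mechanism. This objection stands against the numbers. It does not show that the PPV error can be left out: under another mechanism it would generally still reach the AR.

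A reader might also infer a large distortion. The largest factors need an IRR near 10, where the AR is about 12 case-only SEs from zero and no conclusion about the existence of an excess would change. The follow-up analyses are triggered by the IRR, not the AR. Section 5.5.6 specifies an SE but no AR interval, Section 5.5.3.1 plans a run without the PPV adjustment, and Table 5 discloses the PPV limits. These facts limit the consequences.

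Finally, this could be called detail for the statistical analysis plan. That would hold if Section 5.5.6 left the SE open. Instead it gives the recipe in full, and the recipe lacks a variance source that the protocol itself tabulates.

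**Conclusion.** The point holds in conditional form. As written, the AR standard error for anaphylaxis and GBS includes no contribution from the PPV estimates, and if the PPV scales the AR the SE is too small. The effect is negligible near the null, modest for anaphylaxis with a clear excess, and small for GBS in the scenarios shown. These sizes rest on one PPV for both intervals and on case counts and IRRs that the protocol does not give. The fixed case total is a second, separate understatement. It equals or exceeds the PPV effect in every scenario tabulated except anaphylaxis at IRR 5 with 200 cases, so correcting the PPV alone would leave the SE too small.

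**What to change.** Amend Section 5.5.6 as follows.
- For anaphylaxis and GBS, each bootstrap iteration draws the PPV from a distribution matching Table 5, about Beta(57, 29) and Beta(88, 36). These have means 0.66 and 0.71 and SDs of about 0.051 and 0.041.
- The same draw is used wherever the PPV enters that iteration's IRR and AR. The section should also state how it enters.
- The total number of resampled cases varies across iterations, for example as a Poisson number with mean equal to the observed count.

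This takes a few sentences of text and two random draws per existing iteration, with no new data. The downside is a somewhat larger AR standard error, mainly for anaphylaxis. If the sponsor prefers to keep the PPV constant, the minimum is to state that the SE is conditional on it and to report the AR at the Table 5 limits.

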10.1 Concomitant Vaccination Code List

Concomitant vaccines will be captured using CPT/HCPCS and national drug codes (NDCs). Table E1 outlines the vaccine product and administration codes that will be used to identify persons with concomitant vaccination.

Table E1. Concomitant Vaccine Product and Administration Code List

Concomitant Vaccine	CPT/HCPCS	Vaccine Administration Code	NDC
COVID-19, Bivalent (Pfizer-BioNTech, Moderna)	91312 91315 91313 91314	0124A 0154A 0134A 0144A	N/A
Hepatitis B*	90739 90740 90743 90744 90746 90477 90759 90636 90748	G0010	N/A
Pneumococcal (PCV15/20, PPSV23)	90671 90677 90732	G0009	N/A
Shingrix	90750		58160081912 58160082311 58160082801 58160082803 58160082901 58160082903 50090337200 50090514700

Concomitant Vaccine	CPT/HCPCS	Vaccine Administration Code	NDC		
Tetanust	90696-90698, 90700,90714, 90715, 90721, 90723		00006413301	49281051005	58160080111
			00006413341	49281051105	58160080605
			00008033903	49281054503,	58160080901,5
			00008034001	549281054515	58160081001
			00026063402	49281054605	58160081011
			13533013100-1	49281054658	58160081041,3,6
			13533063402	49281054758	58160081051,2
			13533063420	49281054858	58160081111
			14362011101,3-4	49281056005	58160081141,3,6
			17478013010	49281056101	58160081151,2
			17478013100-1	49281056210	58160081201
			21695041301	49281056258	58160081211
			21695060801,5	49281056410,5	58160081243,6
			21695060901,5	49281056458	58160081251,2
			23490203301,2	49281056488	58160081601,5
			49281021510,5	49281080083	58160081701,5
			49281021558,88	49281081284	58160081811
			49281022510	49281082010	58160084001
			49281022558	50090288300,9	58160084011
			49281027110	54569145800,900	58160084051
			49281027183	54569146000	58160084111
			49281027510	54569387500	58160084146
			49281027810	54569439800,900	58160084201,5
			49281028601,5	54569496900	58160084211
			49281028610	54569548600	58160084232,4
			49281028658	54569608200	58160084243,6
			49281029110	54569638600	58160084251,2
			49281029183	54569642600	58337130101,2
			49281029810	54868057106	63361024310,5
			49281040010,5	54868319700	63361024358
			49281040020	54868339400,1	63361024388
			49281040058	54868349000	63361024510
			49281040088	54868359700	63361024558
49281040089	55045394501	68258893901,5			

Acronyms: Tdap: tetanus, diphtheria, pertussis; Td: tetanus, diphtheria; DTaP: diphtheria, tetanus, pertussis; IPV: inactivated polio vaccine; Hib: haemophilus influenzae type B.

*Captures vaccine combinations including hepatitis B (hepatitis B and A; hepatitis B and Hib).

†Captures vaccine combinations including tetanus (Tdap, Td, DTaP-HepB-IPV, DTaP-IPV-Hib, DTaP-IPV, DTaP-IPV-Hib-HepB). DTaP combinations used in pediatric populations are included to ensure comprehensive capture of concomitant vaccination in claims.

Note: COVID-19, hepatitis B, and PCV vaccines will be captured using CPT/HCPCS product and administration codes only; these vaccines are billed through the Medicare Part B benefit that uses CPT/HCPCS codes for billing. Shingrix and tetanus vaccines will additionally be captured using NDCs as these vaccines are respectively billed through the Medicare Part D benefit or through both Medicare Part B and D benefits; NDCs are used to bill to Part D.

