Historically, adverse events (AEs) following influenza vaccination have been rare. Previous studies conducted in the U.S. and globally over the course of various influenza seasons largely support the safety profile of influenza vaccines showing no elevation in risk associated with several AEs following influenza vaccination.⁽⁴⁻⁹⁾ However, other studies have found associations between influenza vaccines and certain AEs including anaphylaxis, encephalitis or encephalomyelitis, Guillain Barré -Syndrome (GBS) and transverse myelitis.⁽¹⁰⁻¹⁶⁾ For some AEs, observed elevations in risks have largely been attributed to influenza infection.^(4, 17) There is also a potential for the risk of these AEs to be impacted by concomitant vaccination; evidence shows that vaccines such as COVID-19, hepatitis B, pneumococcal, tetanus, diphtheria, pertussis (Tdap), and Shingrix vaccines have displayed an association with some of these AEs when administered independently or concomitantly with other vaccines.⁽¹⁸⁻²¹⁾

For the 2022-23 season, there are multiple influenza vaccines available: Afluria Quadrivalent, Fluarix Quadrivalent, FluLaval Quadrivalent, Fluzone Quadrivalent, Flucelvax Quadrivalent, Flublok Quadrivalent, Fluzone High-Dose Quadrivalent, Fluad Quadrivalent, and FluMist Quadrivalent.⁽²²⁾ Of these vaccines, three are preferentially recommended by the Centers for Disease Control and Prevention (CDC) for use in people aged 65 years or older: Fluzone High-Dose Quadrivalent inactivated vaccine, Flublok Quadrivalent recombinant vaccine, and Fluad Quadrivalent adjuvanted vaccine.⁽³⁾

This document details the specifications for a self-controlled case series (SCCS) study in the U.S. to assess the incidence of select AEs (anaphylaxis, encephalitis or encephalomyelitis, GBS, and transverse myelitis) following administration of influenza vaccines approved for use during the 2022-2023 influenza season. These AEs were chosen because they have been studied in other vaccines. This study will be implemented in the Centers for Medicare & Medicaid (CMS) Medicare claims database among persons aged 65 years and older.

2. Objectives

The objective of this public health study is to assess the safety profile of influenza vaccines administered during the 2022-2023 influenza season in the U.S. population aged 65 years and older. The specific objectives are outlined below.

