- **Primary Objective:** To estimate the incidence rate of the following AEs: anaphylaxis, encephalitis or encephalomyelitis (including acute disseminated encephalomyelitis (ADEM)), GBS, and transverse myelitis after exposure to influenza vaccines in the risk interval, compared to the incidence rate of the AEs in the control interval. Assessment of AEs incidence rates will be performed for all influenza vaccine types combined together (overall), and for high-dose and adjuvanted vaccine groups separately. Vaccine groupings are presented in Table 3.
 - **Follow-Up Objective (if applicable):** If there is a statistically significant association in the primary analysis indicating a potentially increased rate of an AE in the risk compared to control interval, we will evaluate the potential contribution of concomitant (same-day) vaccination with at least one of five other vaccines to the elevated incidence rate for the given AE. The analysis for the specific outcome(s) with a statistically significant result will be stratified by concomitant vaccination status (influenza vaccination alone, and influenza vaccine *with any* same-day concomitant vaccination). Where sufficiently powered, follow-up analyses by combinations of concomitant vaccines may be performed.
 - Concomitant vaccines of interest are listed below.^{1(23, 24)} Table E1 can be referenced for associated vaccine code lists:
 - COVID-19 Bivalent (Pfizer-BioNTech, Moderna)
 - Pneumococcal (PCV15/20, PPSV23)
 - Hepatitis B
 - Tetanus (Tdap, tetanus, diphtheria (Td))
 - Shingrix

3. Data Sources

The study will be performed using the Medicare administrative claims database. The Medicare claims database includes well-defined longitudinal data that captures healthcare service utilization for millions of enrollees across multiple care settings including inpatient, outpatient-emergency department (OP-ED) and outpatient non-ED, professional services non-laboratory and laboratory, and pharmacy settings.

The Medicare Study will include CMS Medicare Shared System Data (SSD) to capture longitudinal healthcare information for persons aged 65 years and older in the study population. Medicare Fee-for-Service (FFS) Part A (inpatient) and Part B (outpatient and physician services) will be used to capture patient's vaccination history, healthcare services, health-related covariates, and diagnoses. Medicare

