5.5.4 Follow-Up Inferential Analysis- Concomitant Vaccination Analysis

5.5.4.1 Incidence Rate Ratio (IRR) Estimation

The follow-up inferential analysis will only be performed for AEs for which a statistically significant elevated incidence rate ratio is observed from the primary analysis. This analysis will be implemented consistently with the primary analysis specified in Section 5.5.3.1, except the analysis will be conducted in two separate subgroups. One subgroup will include persons with an observed influenza vaccination *with any* concomitant (same-day) vaccination, and the other subgroup will include persons with influenza vaccination *without any* concomitant (same-day) vaccination. Where sufficiently powered, follow-up analyses may be performed by combinations of concomitant vaccines.

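### The follow-up 'influenza alone' stratum really means 'none of the five listed vaccines', and one hepatitis B code in the list (90477) looks transposed

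*Protocol*

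**What the plan says.** Section 2 of the protocol sets the follow-up question as the contribution of "concomitant (same-day) vaccination with at least one of five other vaccines to the elevated incidence rate for the given AE". It lists the five: bivalent COVID-19 from two makers, pneumococcal, hepatitis B, tetanus and Shingrix. A footnote says they were chosen because they are recommended at age 65 and older. The same objective says the analysis will be "stratified by concomitant vaccination status (influenza vaccination alone, and influenza vaccine" with any same-day concomitant vaccine.

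Section 5.5.4.1 repeats the primary model, "except the analysis will be conducted in two separate subgroups". One has any "concomitant (same-day) vaccination, and the other subgroup will include persons with influenza vaccination" without any such vaccination. The five-vaccine limit is not restated there.

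The operational rule is in Section 10.1: "Table E1 outlines the vaccine product and administration codes that will be used to identify persons with concomitant vaccination". In Table E1:

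- The COVID-19 row has four product codes and four administration codes, all under a bivalent heading.
- Pneumococcal and hepatitis B each have one administration code for the whole row (G0009 and G0010).
- The hepatitis B product codes are "90739 90740 90743 90744 90746 90477 90759 90636 90748".

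**The concern.** The reference stratum is labelled one way and built another. 'Alone' and 'without any' promise that nothing else was given that day. The rule delivers only that no Table E1 code was found. Nothing in Sections 2, 5.1, 5.5.4.1 or 10.1 excludes people with some other same-day vaccine or sets them apart, so they enter the 'alone' stratum by default.

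The COVID-19 row is where this sits least well with the protocol's own reasoning. Section 1 says that "evidence shows that vaccines such as COVID-19, hepatitis B, pneumococcal, tetanus, diphtheria, pertussis (Tdap), and Shingrix vaccines have displayed an association" with some of these adverse events, and it does not restrict COVID-19 to bivalent products. One report cited there concerns anaphylaxis, a study outcome, after mRNA COVID-19 vaccines from December 2020 to January 2021. Its title is not limited to bivalent products either.

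The follow-up runs only after a significantly elevated primary IRR, and its purpose is to show whether co-vaccination contributes. The 'alone' estimate carries that interpretation. If unlisted same-day vaccines add risk, that risk is credited to influenza vaccine given alone, and the contrast between the strata narrows. The follow-up attributable risk (Section 5.5.6) would inherit the same error.

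**Working it through.** The protocol gives no figure for this point, so there is none to reproduce. Three checks apply.

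**1. Where each kind of person lands under the rule as written**

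| Given on the influenza vaccination date | Table E1 code present? | Stratum |
|---|---|---|
| Influenza vaccine only | No | Alone |
| Plus a listed vaccine | Yes | With any |
| Plus only a vaccine outside the five groups | No | Alone |
| Plus a COVID-19 product other than those listed | No | Alone |

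The last two rows contradict the label. For COVID-19 there is no row-wide administration code to act as a backstop, as G0009 and G0010 do in their rows.

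**2. The code 90477**

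- Range: every other five-digit non-COVID vaccine code in Table 3 and Table E1 lies in 906xx or 907xx. 90477 is the only exception.
- One-swap test: exchanging adjacent digits of 90477 gives 94077, 90747 or 09477, and also 90477 itself, because the last two digits are equal. Only 90747 falls in the range, and it fits between its neighbours 90746 and 90759.
- Order: the list falls at 90746 to 90477 and again at 90759 to 90636. The second fall may reflect combination vaccines placed at the end of the row, since a table note says combinations are included. The documents do not confirm this.
- Consequence if transposed: a dose billed under 90747 together with G0010 is still found, and one billed under 90747 without G0010 goes to 'alone'. If 90477 denotes something that is not one of the five vaccines, a claim bearing it would wrongly move a person into 'with any'.

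**3. Effect on the 'alone' IRR (assumed inputs)**

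Let f be the share of the stratum's baseline cases (cases arising at the control-interval rate) in people who had an unlisted same-day vaccine. It is not simply a share of people. Then

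observed IRR = (1 − f) × IRR_alone + f × IRR_co.

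The protocol gives neither f nor IRR_co, so both are assumed. With IRR_alone = 1.0:

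| f | IRR_co = 1.5 | 2 | 3 | 6 |
|---|---|---|---|---|
| 1% | 1.005 | 1.01 | 1.02 | 1.05 |
| 2% | 1.01 | 1.02 | 1.04 | 1.10 |
| 5% | 1.025 | 1.05 | 1.10 | 1.25 |

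Example: 0.95 × 1 + 0.05 × 3 = 1.10. If the true 'alone' IRR is 1.5 and IRR_co is 3, f = 5% gives 0.95 × 1.5 + 0.05 × 3 = 1.575. If IRR_co equals IRR_alone, the observed value equals the true one at every f.

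**The case against.** The strongest reply is that the five-vaccine restriction is a stated and reasoned choice. Section 2 names the vaccines, the footnote gives the basis, and the descriptive analysis in Section 5.5.2 points back to Section 2. Read that way, 'without any' means none of the five, and only the label is loose. This stands as far as the 'with' stratum is concerned. A reader might infer that leaving out all other vaccines was an oversight, and the documents do not support that. But a reason for choosing which vaccines to study is not a reason for counting recipients of other vaccines as having had influenza vaccine alone. The protocol also aims at comprehensive capture elsewhere: Section 5.1 requires Part D enrolment for it, and Table E1 includes paediatric combinations for it.

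The reply on size also largely stands. Section 1 attributes risk only to the five classes, so harm from vaccines outside them is an assumption. The protocol does not say which other COVID-19 formulations were given between August 1 and November 12, 2022, or how often on the same day as influenza vaccine. At f up to 2%, the shift for IRR_co up to 6 is at most 0.10 on a true IRR of 1.0. That is no larger than the claims-delay bias of (1/0.9) − 1 = 11% discussed in Section 5.5.1.

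On 90477, a reader might take the code as proven wrong. It is not. The documents do not say what it denotes, the row is out of order at a second place, and other characters in the text version of Table E1 are misread, so a reading error cannot be excluded. G0010 would also recover part of any loss, and a stray code works in the opposite direction to a missed one.

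**Conclusion.** The point holds as a mismatch between label and definition. As written, people with an unlisted same-day vaccine, including another COVID-19 formulation, are analysed as influenza alone. The size is unknown from the documents and probably small: about 1.01 to 1.10 against a true 1.0 for f of 1% to 5% and IRR_co of 2 to 3, all assumed. It is zero if the unlisted vaccine adds no risk.

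The code 90477 appears transposed from 90747. That is a strong inference, not an established error, and it calls for verification.

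It would be tempting to conclude that the study's main safety result is at risk. It is not. The primary IRRs and primary attributable risks do not use concomitant status. What is touched is the conditional follow-up analysis with its attributable risk; the descriptive row on concomitant vaccines is affected only through the code list. The change is still worth making because it is specific and cheap, and it protects the one estimate the follow-up depends on.

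**What to change.** - Keep the five vaccines as the definition of the 'with' stratum.
- In Sections 5.5.4.1 and 10.1, define 'influenza alone' as no other vaccine product or administration claim of any kind (CPT/HCPCS or NDC) on the influenza vaccination date. Include in that check the other COVID-19 codes valid between August 1 and November 12, 2022.
- Leave people whose only other same-day vaccine is unlisted out of both strata, and report how many there are.
- If the wider check is not adopted, at minimum rename the stratum 'none of the five listed vaccines' in Sections 2 and 5.5.4.1.
- Verify 90477 against the code book and correct it to 90747 if confirmed.

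The cost is a wider code search in claims already held, edits to two sections and one table, and a very small loss of cases from the 'alone' stratum. Renaming alone costs nothing but leaves the misclassification in place.
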